4.3 Subject Recruitment, Enrollment and Screening

Patients with a diagnosis of PSC will be recruited by the study staff in the Division of Gastroenterology and Hepatology at Mayo Clinic) and enrolled in the study if satisfying the above inclusion and exclusion criteria. A total of 15 patients will be enrolled.

4.4 Early Withdrawal of Subjects

Study participants may decide to withdraw from the study at any time; in such case, they will be asked to notify the study team so that they may be advised as to whether any additional tests may be needed to be performed for their safety. Study investigators may withdraw participants from the study at any time if it is considered in a patient's best interest or if a patient does not follow the study protocol. Additional details are provided below.

4.4.1 When and How to Withdraw Subjects

Participants will be withdrawn from the study if they experience a CTCAE 4.0 criteria grade 3 or higher adverse event, are unable to adhere to the study protocol, inadvertently become pregnant during the study (in which case they will be referred to their primary physician for obstetric care), or experience treatment failure as described in section 3.4 above.

Participants may voluntary withdraw from the study for any reason. Patients who withdraw from the study (or decline participation) will not be penalized in any way. Specifically, they do not have to be in this study to receive or continue to receive medical care from Mayo Clinic.

4.4.2 Data Collection and Follow-up for Withdrawn Subjects

Patients who withdraw from (or complete) the study will be followed for a minimum of 2 weeks (to ensure safety) as part of the study in addition to longitudinal routine clinical care.

5 Study Drug

5.1 Description

The study drug will be administered in the form of a capsule (softgel).

5.2 Treatment Regimen

Participants will receive one 750 mg CuraMed® BCM-95 curcumin softgel (EuroPharma, Inc.) by mouth twice a day for 12 weeks.

5.3 Method for Assigning Subjects to Treatment Groups

This will be an open-label pilot study with one treatment group.

5.4 Preparation and Administration of Study Drug

The study drug will be prepared by EuroPharma, Inc. The drug will be stored in the Mayo Clinic Pharmacy and dispensed in the Mayo Clinic Hepatology Clinic, Division of Gastroenterology of Hepatology, by the study coordinator (and/or co-investigators).

5.5 Subject Compliance Monitoring

Adherence will be tracked by the study coordinator using telephone calls weekly. The patient will be asked specifically about compliance with the study drug schedule. If the patient is not deemed by the study investigators to be compliant based on phone call assessment, the patient will be withdrawn from the study but still followed (intention to treat). A decision regarding non-compliance will be determined by the following: the patient has acknowledged being off the study drug for more than two weeks without reason or has been unable to be contacted by the study coordinator or study physician for greater than 6 consecutive weeks.

5.6 Prior and Concomitant Therapy

Potential participants will be excluded if they receive or have received:

- Treatment with any investigational agents within three months prior to or during the study.
- Treatment with UDCA, systemic corticosteroids, colchicine, methotrexate, cyclosporine, chlorambucil, pentoxifylline, or tacrolimus within three months prior to or during the study.

5.7 Packaging

The study drug will be packaged with a label stating "Caution: New Drug--Limited by Federal (or United States) law to investigational use only", instructions for use, i.e. "Take one 750 mg CuraMed® curcumin softgel by mouth twice a day", and the Mayo Clinic protocol number. The amount of softgels will also be written on the label (12 week supply, i.e. 168 softgels).

5.8 Blinding of Study

NA—open-label study.

5.9.2 Storage

The study drug will be stored in a 4°C refrigerator in the dark in the institutional research pharmacy until it is dispensed. This is a secure location with limited access to prevent unintended or unauthorized use. No special handling precautions are otherwise necessary.

5.9.3 Dispensing of Study Drug

A 12 week supply of the study drug will be assigned and dispensed to each study participant. Drug reconciliation checks will be performed by the study team and documented in the medical record. Subjects will be requested to mail in any unused study drug if unable to return for the 12 week visit.

Return or Destruction of Study Drug

At the completion of the study, there will be a final reconciliation of drug shipped, drug dispensed, drug returns, and drug remaining. This reconciliation will be documented in the study file. Study drug destroyed on site per Mayo Pharmacy policy.

6 Study Procedures

Study procedures are summarized in section 3.1 as well as in Table 1.

Screening Visit (-28 to Day 0)

Screening assessments will be completed within 28 days of the baseline/Day 1 visit.

The following procedures will be performed and documented:

- Obtain signed informed consent
- Determine inclusion eligibility
- Obtain medical history
- Perform complete physical examination
- Obtain body height and weight
- Obtain vital signs (resting blood pressure, pulse, respiratory rate and temperature)
- Obtain details of concomitant medications
- Obtain blood samples for
 - Alkaline phosphatase
 - AST

ALT
Total bilirubin
C-reactive protein
Complete blood count (CBC)
INR
Sodium
Creatinine
Albumin
Stored serum
Serum pregnancy test for females of childbearing potential only
Questionnaires
Health status
Pruritus
Fatigue

Subjects meeting all of the inclusion criteria and none of the exclusion criteria will return to the clinic for the Baseline/Day 1 visit.

Treatment Assessments

Baseline/Day 1 Visit

Dispense study medication
Instruct the subject on the packaging, storage and administration of the study drug
If indicated, observe the subject take the first dose of the study drug

Week 3 (+- 7 days)

Obtain blood samples for
Alkaline phosphatase
AST
Total bilirubin
C-reactive protein
Complete blood count (CBC)
Creatinine
Albumin

Phone call or visit to assess for AEs, concomitant medications, and study drug compliance. Note a local laboratory can be used for obtaining the blood samples if subject is unable to return to Mayo.

Week 8 (+- 7 days)

Phone call to assess for AEs, concomitant medications, and study drug compliance. Note a local laboratory can be used for obtaining the blood samples if subject is unable to return to Mayo.

Week 12 (+- 7 days) or Early Termination

Obtain blood samples for
 Alkaline phosphatase
 AST
 ALT
 Total bilirubin
 C-reactive protein
 Complete blood count (CBC)
 INR
 Creatinine
 Sodium
 Albumin
 Stored serum

Questionnaires
 Health status
 Pruritus
 Fatigue

Phone call to assess for AEs, concomitant medications, and study drug compliance. Note a local laboratory can be used for obtaining the blood samples if subject is unable to return to Mayo. Questionnaires can be mailed to subject if unable to return to Mayo or respond over the phone. Remaining study medication can be returned by mail to study team.

Post Treatment Assessment Week 14 (+- 7 days) (2 weeks after stopping study medication)
 Phone call to assess for AEs, concomitant medications

Table 1. Patient evaluation and study procedures

n=20 patients with PSC	Entry	3 weeks	8 weeks	12 weeks	2 weeks after study completion (i.e. 14 weeks)
Medical history and physical examination	X				
Serum laboratory tests*					
ALK	X	X		X	
AST	X	X		X	
ALT	X			X	
Total bilirubin	X	X		X	
C-reactive protein	X	X		X	
Complete blood count	X	X		X	
INR	X			X	
Creatinine	X	X		X	
Sodium	X			X	
Albumin	X	X		X	
Stored serum **	X			X	
Pregnancy test ***	X				
Questionnaires					

Health status	X			X	
Pruritus	X			X	
Fatigue	X			X	
Phone calls†		X	X	X	X

* At study entry, approximately 2 teaspoons of blood will be collected for biochemical testing. At 3 and 12 weeks, approximately 1 teaspoon will be collected for biochemical testing.

**Serum collected at baseline and at the conclusion of the study will be stored for potential future assays to explore mechanisms of action in the pathogenesis of PSC if the study drug seems beneficial.

***For female patients only.

†Will be performed for safety and compliance monitoring as described above and documented accordingly.

7 Statistical Plan

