3.2 Primary Study Endpoints

The primary study endpoint in this study will be treatment success, as determined by the proportion of PSC patients who experience clinically significant improvement in Alkaline Phosphatase, as defined by: 1) a $\geq 40\%$ reduction in serum Alkaline Phosphatase (as compared to baseline value)³⁷ or 2) a decrease in serum Alkaline Phosphatase to less than 1.5 times the upper limit of normal following 12 weeks of curcumin treatment.³⁸

Notably, serum Alkaline Phosphatase values have been repeatedly associated with disease response and prognosis,³⁹⁻⁴¹ thus this readily measured biochemical test is an important endpoint and biomarker in studies of patients with PSC.

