4.1 Inclusion Criteria

Inclusion criteria will be as follows:

- Diagnosis of PSC established by all of the following criteria:^{27, 43}
 - ALK $>1.5x$ upper limit of normal for at least 6 months prior to study enrollment

- Cholangiography demonstrating intrahepatic and/or extrahepatic biliary dilation, beading, and/or strictures consistent with PSC
- Age 18-75 years
- Male or female sex
- Women of child-bearing potential willing to use birth control for the duration of the study
- Informed consent provided by the patient for study participation

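### Baseline ALK is undefined and rests on one screening draw, entry and success share the 1.5x ULN line, and the 5% null is not shown to absorb the resulting spontaneous successes

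*Combined protocol and SAP*

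**What the plan says.** - **Pre-dose sampling.** In section 6 the screening visit runs from day -28 to day 0 and includes ALK: "Screening assessments will be completed within 28 days of the baseline/Day 1 visit". The Baseline/Day 1 list opens with "Dispense study medication", continues with instructions and an optional observed first dose, and contains no blood test. Table 1 has one pre-dose ALK column, Entry, with the footnote "At study entry, approximately 2 teaspoons of blood will be collected for biochemical testing". Later ALK draws are at weeks 3 and 12.
- **Entry.** Section 4.1 requires ALK above 1.5 times the "upper limit of normal for at least 6 months prior to study enrollment". It does not say how many values establish this.
- **Success.** Section 3.2 accepts either a fall of at least 40% from baseline or "a decrease in serum Alkaline Phosphatase to less than 1.5 times the upper limit of normal" after 12 weeks. The second limb has no minimum fall. No section says which measurement is the baseline.
- **Comparator.** Section 5.3 has one treatment group. Section 7.1 tests against a historical rate of 5%, described as the rate at which patients with ALK raised for more than 6 months meet either limb spontaneously. The alternative is 30%, with 15 patients.

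**The concern.** Patients are selected for being above a line and then scored for being below it. ALK varies from visit to visit, so someone whose usual level is just above 1.5x ULN can be below it at week 12 with no treatment effect. A screening value that happens to be high also makes a 40% fall easier to reach. Both limbs therefore lean towards success when baseline is one selected reading.

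Without a control arm, the 5% null is the only correction. If the true no-effect rate under this sampling scheme is higher than 5%, the exact test rejects too often, and a positive pilot, which section 3.1 makes the basis for a larger trial, could partly reflect ordinary variation.

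**Working it through.** **1. The plan's test.** Let X be the number of successes in 15. At p = 0.05, P(X >= 3) = 1 - (0.4633 + 0.3658 + 0.1348) = 0.036. At p = 0.30, P(X >= 3) = 1 - (0.0047 + 0.0305 + 0.0916) = 0.873. So the exact two-sided test rejects at 3 or more, with 87.3% power against a stated figure of about 90%; that gap is a separate matter. Placing 0.025 in the upper tail moves the cut-off to 4 (error 0.55%, power 70.3%). The 30% go-forward bar is 0.30 x 15 = 4.5, so 5 successes. All three cut-offs are carried below.

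**2. The shared line.** The fall needed is 1 - 1.5/baseline: 3.2% from 1.55x ULN, 6.3% from 1.6x, 14.3% from 1.75x. For a stable patient with usual level 1.6x ULN and lognormal visit noise, P(week 12 < 1.5x) = Phi(ln(1.5/1.6)/s), with s = sqrt(ln(1 + CV^2)). At CV 10%: Phi(-0.0645/0.0998) = 26%. At CV 30%: Phi(-0.0645/0.2936) = 41%.

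**3. No-effect success rate for the whole sample (simulation).** Assumptions, none of them document figures:
- usual ALK is lognormal between patients, log-SD 0.5, with median 2.0x or 2.5x ULN before the entry gate;
- visit noise is independent and lognormal;
- one earlier value stands in for the 6-month rule, and both it and the screening value must exceed 1.5x ULN;
- baseline is the screening value;
- success is week 12 <= 0.6 x baseline or < 1.5x ULN.

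| Within-patient CV | Median 2.5x ULN | Median 2.0x ULN |
|---|---|---|
| 10% | 1.8% | 3.0% |
| 15% | 3.5% | 5.2% |
| 20% | 6.8% | 8.9% |
| 25% | 11.1% | 13.4% |

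At median 3.0x ULN the rate is 1.1%, 2.5% and 5.6% at CV 10%, 15% and 20%. At CV 20% and median 2.0x, 6.3% of patients meet the below-1.5x limb and 3.8% the 40% limb, so both contribute.

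**4. Effect on the trial's error rate at CV 20%.** Apply P(X >= r) for n = 15 to the unrounded rates for medians 2.5x and 2.0x.

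| Cut-off | At the 5% null | At the simulated rates |
|---|---|---|
| >= 3 | 3.6% | 7.9% to 14.2% |
| >= 4 | 0.5% | 1.6% to 3.8% |
| >= 5 | 0.06% | under 1% |

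**5. What drives it.** Using a Day 1 value alone as baseline, in place of screening, changes the no-effect rate by at most 0.4 points (17.8% to 17.5% at CV 30%, median 2.0x; 8.8% either way at CV 20%). Averaging two pre-dose values does more: at CV 20%, 6.8% becomes 5.5% and 8.9% becomes 7.6%. With those rates, P(X >= 3) is 1 - (0.4280 + 0.3737 + 0.1522) = 4.6% and 1 - (0.3055 + 0.3770 + 0.2170) = 10.0%.

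**The case against.** The strongest reply is that the plan already has two safeguards.

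First, entry needs six months of elevation, not one high reading. This stands and matters. If entry rested on the screening value alone, the rate at median 2.0x ULN and CV 20% would be 12.6%; one earlier qualifying value brings it to 8.8-8.9%. More historical values would lower it further.

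Second, spontaneous success is what the 5% null is for, so only an excess over 5% is bias. This also stands in principle, and section 7.1 calls the figure conservative. But 7.1 does not say over what interval, from how many measurements or with what starting threshold the 5% arose, so the documents do not show that it matches this design.

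The go-forward bar of 5 in 15 is also well protected, as the last line of the error table shows.

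Three stronger readings are tempting and not supported:
- *That regression to the mean is in fact being scored as curcumin success.* This needs a within-patient CV that the documents do not give. At 10% there is no excess over 5%.
- *That a patient already below the line on Day 1 is a success before treatment can act.* Section 3.2 judges success after 12 weeks, so that patient must still be below the line then.
- *That the 28-day window or the missing Day 1 draw is itself the error.* A screening window of that length is not a fault, and moving the single baseline to Day 1 changes almost nothing.

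**Conclusion.** The point holds as a design weakness of moderate size, not as a demonstrated bias. Baseline is undefined, the schedule offers one pre-dose value, entry and success use the same line with no minimum fall, and the 5% null is not tied to that combination. Under the stated model the no-effect rate is at or below about 5% up to CV 15% and exceeds it from about CV 20%. At CV 20% the false-positive risk at 3 or more successes is 7.9-14.2% instead of 3.6%; at 4 or more it stays below 5%, and at 5 or more below 1%. The size rests on the assumed CV, the ALK distribution and a single earlier qualifying value. A change is worth making because it is cheap, but the plan's go-forward decision is not undermined.

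**What to change.** 1. In section 3.2, define baseline ALK for the primary endpoint as the mean of two pre-dose values, each in multiples of its laboratory's ULN. Use either screening plus a pre-dose draw at the existing Day 1 visit or, with no new draw, screening plus the latest value documented for the 6-month criterion. In the simulation at CV 20% both options give 5.5% (median 2.5x ULN) and 7.6% (median 2.0x).
2. Count the below-1.5x limb only when that mean exceeds 1.5x ULN. Because this is a scoring rule and not an entry criterion, eligibility and dosing need not wait for a Day 1 result. With the no-draw option it is met automatically if both values exceed the line.
3. Report successes by limb.
4. In section 7.1, state the interval, number of measurements and starting threshold behind the 5%, or say that these are unknown.

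Cost: one ALK assay per patient (15 in all) or none, and a slightly less favourable success rate. Averaging loses at most about 2 points in the per-patient response rate if ALK truly falls by 35%. It reduces the bias but does not remove it, so the 5% null still needs its justification.

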3.1 General Design

We propose to conduct an open-label pilot study to preliminarily assess the efficacy and safety of oral curcumin in adult patients with PSC. Fifteen patients with PSC will receive one 750 mg CuraMed® softgel (EuroPharma, Inc.) by mouth twice a day for 12 weeks. Of note, each 750 mg CuraMed® softgel supplies 500 mg of highly bioavailable BCM-95 curcumin. A positive study, based on significant improvement in serum liver biochemistries, will establish the basis for further evaluation of curcumin in a larger, longer-term clinical trial.

Table 1 in section 6 summarizes the patient evaluation and study procedures. Briefly, prior to study entry, a complete history will be obtained and physical examination performed. Serum Alkaline Phosphatase, AST, total bilirubin, albumin, C-reactive protein, complete blood count, and creatinine will be measured. A blood pregnancy test will be performed on female patients of child bearing potential. Standardized questionnaires regarding health status (SF-36 Health Survey and Chronic Liver Disease Questionnaires), fatigue (Fisk Fatigue Impact Scale) and pruritus (5-D Pruritus scale) will be completed by participants at baseline and at 12 weeks. Phone calls will be made to participants weekly during the study, at completion of the study (i.e. at 12 weeks of therapy) and/or early termination, and at two weeks after completion of the study to monitor for any adverse events or effects of the study drug. Study staff will specifically inquire about local and systemic adverse effects including gastrointestinal upset, nausea, diarrhea, signs of anemia (e.g., weakness, fatigue), and rash; during weekly phone or in person

interviews. Participants will be instructed to contact study nurse coordinators with the development of any possible symptoms related to therapy.

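### The only scheduled pregnancy test can be up to 28 days old when the 12-week drug supply is handed out, and no repeat is scheduled on Day 1

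*Combined protocol and SAP*

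**What the plan says.** Section 6 has a screening visit followed by a separate Baseline/Day 1 visit. On the interval between them it states: "Screening assessments will be completed within 28 days of the baseline/Day 1 visit". The screening blood samples include "Serum pregnancy test for females of childbearing potential only". Section 3.1 describes the same test among the procedures done before study entry: "A blood pregnancy test will be performed on female patients of child bearing potential". Table 1 marks one pregnancy test, in the Entry column, with the footnote "For female patients only". It marks none at weeks 3, 8, 12 or 14.

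Eligibility is settled before the second visit: "Subjects meeting all of the inclusion criteria and none of the exclusion criteria will return to the clinic for the Baseline/Day 1 visit". The Day 1 list then has three items: hand out the drug, explain how to use it, and "If indicated, observe the subject take the first dose of the study drug". Under section 5.9.3 each participant is given the whole 12-week supply, which section 5.7 counts as 168 softgels.

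Three other provisions bear on pregnancy. Section 4.2 excludes it, section 4.4.1 withdraws a participant who becomes pregnant during the study, and section 4.1 has the inclusion criterion "Women of child-bearing potential willing to use birth control for the duration of the study".

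**The concern.** Pregnancy is an exclusion that can newly apply between screening and first dose, and the woman may not know of it. The plan tests for it once, before an interval of up to four weeks, and then hands out the full course without testing again. A site that follows the listed procedures exactly could start an excluded patient on study drug.

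At stake is avoidable exposure of an unrecognised pregnancy. The tolerability statements in sections 1.4 and 1.5 do not settle the matter, because they do not mention pregnancy. This is a patient-safety point about the visit schedule. It does not touch the alkaline phosphatase endpoint, the sample size or the error rates.

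**Working it through.** No statistical formula applies. The check is a reading of the schedule plus day counts.

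**Inputs**
- Longest interval from screening assessments to Day 1: 28 days (section 6).
- Latest screening day: Day 0 (section 6, screening visit label).
- Supply and regimen: 168 softgels, two a day (sections 5.7 and 5.2).
- Pregnancy tests scheduled: one, at screening (section 6), marked at Entry (Table 1).

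**Where the test falls.** Taken alone, the Entry column of Table 1 could mean Day 1. Section 6 rules that out by listing the test under the screening visit and not under Day 1. Section 3.1 agrees, since it puts the test before study entry.

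**Age of the test at first dose**
- Shortest: Day 1 − Day 0 = 1 day.
- Longest: 28 days, the stated limit.

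**Dosing period**
- 168 softgels ÷ 2 per day = 84 days, which agrees with 12 weeks × 7 days = 84 days.

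**Longest span resting on one test**
- 28 + 84 = 112 days.
- Share of that span on treatment: 84 ÷ 112 = 75%.

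**Do the other provisions detect a pregnancy at Day 1?**
- Birth control (4.1) makes conception less likely. It does not reveal a contraceptive failure, or a pregnancy too early for the screening test.
- Withdrawal on pregnancy (4.4.1) acts only once a pregnancy is known, and no test is scheduled to reveal one.
- The weekly calls (3.1) run during treatment, so they come after the first dose. The adverse effects that staff are told to ask about do not include pregnancy. The week 3 contact is described as "Phone call or visit to assess for AEs, concomitant medications, and study drug compliance", and its listed blood samples include no pregnancy test.

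**With a test on Day 1**
- Longest age of the last test at first dose: 28 days → 0 days.
- Dosing days without a scheduled test: 84 → 84, unchanged.
- Sample size, power and significance level: unchanged.

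**The case against.** The strongest reply is that this is a design preference. The 28-day window is explicit and applied consistently, nothing in the document contradicts it, and the document states no standard that requires a test at dispensing. Consent is obtained at screening, so the birth-control commitment can reasonably be read to cover the interval to Day 1. If that commitment and the withdrawal rule are trusted for 84 days on drug, why not for 28 days before it? Most of that is fair, and it is why the point is optional. What survives is that Day 1 is where exposure begins, the visit already takes place in clinic, and none of these provisions can find a pregnancy. Testing during treatment is a separate decision that this point does not reopen.

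A reader might also infer stronger things that the documents do not support.
- *That patients who became ineligible for any other reason could properly be dosed.* They could not. Sections 4.2, 4.3 and 5.6 still bind on Day 1, several exclusions run on into the study by their own terms, and the Day 1 list is not said to be complete. An interval eligibility check would be checklist detail.
- *That a probability of exposure can be given.* The documents give neither the number of women of child-bearing potential nor a conception rate. Any figure would rest wholly on assumed inputs, and would count conceptions that a urine test would miss.
- *That a Day 1 test closes a 28-day window of undetected pregnancy.* The change from 28 days to 0 is in the age of the test. A very recent conception can still be missed.
- *That curcumin has been shown to harm a pregnancy.* The documents contain no such data. The exclusion shows caution only.

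**Conclusion.** The point holds as a low-severity safety gap. One pregnancy test is scheduled, it may be 1 to 28 days old at first dose, and no section schedules a repeat before the 12-week supply is handed out. A woman who conceived after screening, or whose very early pregnancy was missed then, could start study drug despite the exclusion.

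The day counts come straight from the plan. The conclusion assumes that the Day 1 list is followed as written; staff may well ask or test in practice. That the expected number of cases is near zero is a judgement from the small enrolment of 15 and the birth-control criterion, since the documents give no rate. Most of the time resting on the single test, 84 of at most 112 days, is on treatment and would remain so after the change.

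**What to change.** In the Baseline/Day 1 list of section 6, ahead of the dispensing step, add: *Urine pregnancy test in women of child-bearing potential; do not dispense if positive.* Show the test in Table 1 under a Day 1 column.

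The cost is one inexpensive test and a few minutes at a visit that already exists, plus an occasional lost enrolment. No extra visit or blood draw is needed.
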